423 to 24. The additional six clinics are necessary because of the lower than anticipated participant
424 enrolment numbers due to COVID 19 pandemic and healthcare worker's strike that affected the
425 numbers of pregnant women visiting health facilities and consequently our study accruals in the year
426 2020 and 2021. Using a stratified randomized design, we will recruit HIV-negative women in balanced
427 numbers to HIV-positive women (1:2) each month, to ensure that these two groups are balanced over
428 time. Given our experience in the R34 pilot study (which had more stringent eligibility criteria), we
429 conservatively estimate a 75% participation rate for male partners in the study (target sample N=800
430 couples). If we subsequently experience as much as 17% loss-to-follow-up of couples (based on the
431 14% we experienced in the R34 pilot), we will still have approximately 664 couples (221 couples in
432 each randomized group) for analysis. With a loss-to-follow-up rate as high as 20% (leaving 640
433 couples), we will still have strong power to detect differences in our primary couples testing outcome
434 (Table 2).

435
436 Two groups of n=30 women each will be purposively selected from enrolled participants and invited to
437 participate in in-depth qualitative interviews. The samples will include women who are HIV-positive or -
438 negative and who participated in the different arms of the trial. One group will include women ≤24 years
439 of age, and the other group will comprise women of any age who have reported IPV at any time during
440 the trial.

441
442 **Recruitment and enrollment:** Pregnant women presenting at ANC clinics who meet study inclusion
443 criteria will be asked if they would like to participate in a study about approaches for supporting
444 pregnant couples on family health issues (including HIV) during pregnancy and postpartum. If
445 interested, informed consent will be obtained for study participation and for contacting her male partner.
446 Those interested in participating but not comfortable with face- to- face contact due to COVID -19
447 pandemic will be asked to participate remotely via the phone after safety and privacy has been
448 ascertained.

449
450 Postpartum women enrolled in the trial who are eligible to participate in the in-depth qualitative
451 interviews will be contacted by a researcher and invited to participate in an interview (at least 12
452 months postpartum for the young women and ≤24 months postpartum for the women with IPV) at a
453 private location at a date/place of her choosing, after going through the informed consent process
454 described below. Interviews will be led by experienced qualitative interviewers in a local language (Luo,
455 Kiswahili, or English) using IRB-approved interview guides developed by the research team. To
456 contribute to the achievement of Aim 2, these interviews will explore topics that influence health
457 behaviors and outcomes, such as reproductive health, relationships, HIV, and IPV.

458
459 **Obtaining informed consent:** A lay health worker will consent eligible women and their male partners
460 separately. As was done in the R34 pilot study, with the woman's permission we will subsequently
461 contact her primary male partner, arrange to meet with him in a community location, and conduct
462 informed consent and the baseline questionnaire. For participants who wish to enroll in the study but
463 prefer virtual/remote participation, we will conduct consenting process on the phone. The study staff
464 shall read the consent word for word and verify the participant's understanding before obtaining verbal
465 consent. Verbal consent shall be taken by asking the participant to repeat the participant declaration
466 statement written in the tail end of the consent as the staff audio records. All participants choosing to be
467 consented remotely will be informed of recording their declaration to participate and the consent form
468 will be kept safely for signing by the participant when COVID-19 spread is brought under control. These
469 initial sessions will also include screening for IPV based on our team's existing protocols, and all
470 participants will receive information about available services.[141]Participants reporting severe IPV in

471 the past 6 months will not be included in the randomized part of the study, since participation in a
472 couples intervention may not be appropriate for this group. All participants will be asked to provide
473 informed consent for data abstraction from their medical records.

474
475 Women who are eligible and interested in participating in the in-depth qualitative interviews will undergo
476 the informed consent process with study staff and sign a consent form specific to the interview.
477

478 **Randomization:** We will recruit pregnant women attending ANC clinics to participate in the study until
479 we have achieved a sample size of 800 women (two-thirds HIV-positive at baseline) and 800 male
480 partners. Women will complete baseline questionnaires at the ANC clinic and men will be asked to
481 complete the questionnaire in a community location. After baseline interviews have been completed
482 with both partners, we will randomize couples to one of the three approaches to increase couple
483 engagement in HIV prevention and maternal and child health. Couples will receive a sealed envelope
484 labeled with their newly assigned study ID numbers, which will contain their random assignment. If the
485 participants are not comfortable with face-to-face contact during the COVID-19 pandemic,
486 randomization can be carried during a joint phone call with the couple, in which case the couple will be
487 informed of the envelope randomly picked by the study staff out of the container, and their randomly
488 assigned study arm. Random assignments will be computer generated and will be stratified by clinic
489 and couple HIV status. Blocked randomization with randomly permuted block sizes will be used to
490 assure approximately equal numbers in each study arm and in each HIV status group in any given time
491 period. Based on our prior experience in the R34 pilot study, at the end of this process we expect to
492 have at least 267 couples (both male and female partners consented and enrolled) in each study arm
493 (178 in which the woman is HIV-positive at baseline and 89 in which the woman is HIV-negative at
494 baseline).

495 **Study arms:** After randomization, a lay health worker will obtain detailed locator information (including
496 cell phone contacts). If they were randomized to the home visit intervention arm, the worker will consult
497 with them about optimal times for a home visit. As described above, the intervention arm will consist of
498 5 home visits conducted together by one female and one male lay health worker. The HIV self-test kit
499 arm will consist of distribution of pairs of self-test kits to women at up to 4 time points (twice during
500 pregnancy and twice after the birth). The standard care arm will offer standard clinic-based services,
501 including giving the pregnant woman a letter for her male partner inviting him to the clinic, and the
502 option for women and partners to return to the clinic for male partner HIV testing or CHTC (although our
503 past clinical experience in this setting and the results of the R34 study suggest uptake of these services
504 is low).

505 **Data collection and measures:** Data will be collected from multiple sources (see below and Table 1):

- 506 *o Baseline questionnaires* with all study participants will be conducted with women and male partners
507 through phone or in-person assessment depending on their preference during this challenging period
508 of COVID-19. These questionnaires will assess baseline measures, including socio-demographic
509 characteristics of both partners, couple relationship measures, and stigma. These measures, which
510 were used successfully in the R34 pilot, will be interviewer-administered on tablets in the participant's
511 preferred language (Swahili, Luo, or English), as per procedures piloted in the R34.
- 512 *o Brief phone-based assessment of HIV testing uptake and results will occur at 8 weeks after study*
513 *enrollment (during pregnancy) and around 6 months after the birth:* All participants (women and men)
514 will be contacted via mobile phone and asked to respond to a brief confidential survey on HIV testing
515 (individual or couples) and results 8 weeks after study enrollment and around 6 months after the birth.
516 This assessment will capture in more "real-time" any HIV testing behavior that occurs before the first
517 follow-up questionnaire at 3 months after the birth, and between 3 and 12 months after the birth.
- 518 *o Follow-up questionnaires* with women and male partners will occur at 3 months after the birth (after 6-
519 week home visit) and around 12 months after the birth (during the 4 weeks following the final 12-
520 month home visit). Follow-up questionnaires will assess the same constructs as at baseline, as well
521 as process and outcome measures, and be administered on tablets in the participant's preferred
522 language during research visits or through phone by gender-matched independent interviewers.

523 ○ *Brief phone 18-month assessments* will capture infant HIV status, couples testing behavior, and viral
 524 loads.
 525 ○ *Medical records*: Medical records will be abstracted to obtain objective (non self-report) data on
 526 healthcare utilization and health outcomes for all participants in the study.
 527 ○ A *couple visit form* will be filled by lay health workers at each couple visit. The form will include
 528 information on topics covered, CHCT uptake and result, assessments of negative life events,
 529 including IPV (conducted with women and men individually),[142] other services provided, and
 530 process measures. This form, along with records of observations of visits by supervisors, will be used
 531 to assess intervention fidelity.
 532 ○ *Qualitative interviews*: Utilizing one-to-one interviews, we will qualitatively explore experiences and
 533 perceptions of the home-based couples intervention, as well as other influences on health behaviors
 534 and outcomes of younger women and of women experiencing IPV.
 535

TABLE 1. Factors to be Assessed in Data Collection

	Factors	Study measurements	Group and timing
PREDISPOSING FACTORS	Socio-demographics	Age, education, literacy, ethnicity, religion, occupation	All participants at baseline and follow-ups
	Relationship characteristics	Marital status, type of union (monogamous/polygamous), relationship duration	
	Household conditions	House type, ownership of household goods, persons living in household, food insecurity, alcohol use (ref AUDIT-C)	
	Pregnancy & fertility	Parity, gravidity, number of living children	
TRANS-FORMATION OF COUPLE	Couple relationship dynamics	Relationship Satisfaction[143], Dyadic Trust[144], Couple communication[145], Interpersonal closeness[146], Sexual Relationship Power Scale[147], Commitment[148]	All participants at baseline and follow-ups
MOTIVATION AND COUPLE COPING	Disclosure	Reports of disclosure to others from both partners[149]	
	HIV-related couple	Male partner support for MCH specific, social support[150], Couple communal coping[151], Network of Relationships Social Provision Scale (ref)	
OTHER POTENTIAL MODERATORS AND MEDIATORS	Pregnancy intendedness	One item measure of the intendedness of the current pregnancy[152]	All participants at baseline and follow-ups
	Perceptions of stigma	Anticipated stigma and perceived community HIV-related stigma scales[153, 154]	
	Stigma experience	Anticipated, enacted, and internalized HIV-related stigma[155]	
	IPV	Dyadic version of WHO intimate partner violence measure[156]	
	HIV treatment beliefs	Adaptation of the Beliefs about Medications Questionnaire[157]	
	Depression	PHQ-8[158]	
COUPLE HIV TESTING (PRIMARY OUTCOME)	Anxiety	GAD-7[159]	
	Couple HIV testing	Couples HIV testing uptake during observation period (Y/N)*	
	HIV re-testing	Re-testing for HIV during pregnancy and postpartum *	
	New male HIV+ tests	Number of new HIV+ test results of male partners*	
HEALTH CARE UTILIZATION	Discordant couples	Number of new serodiscordant couples identified	
	PMTCT practices	Mother's use of ARVs for PMTCT *, Prophylactic ARVs for the infant *, infant feeding practices	
	Use of MCH services	Number of ANC visits*, Childbirth with a skilled attendant (Y/N), Postnatal check-ups*	
	PREP uptake	Initiation of PrEP	
	Woman's HIV care linkage and engagement	Time to linkage in HIV care, *Enrollment in HIV care (Y/N), *Self-reported ART adherence, [160] Number of HIV visits*	
	Man's HIV care linkage	Time to linkage in HIV care, * Enrollment in HIV care (Y/N), * Self-reported ART adherence, [160] Number of HIV visits*	
	Infant HIV testing	Date and result of infant HIV test *	
	Intervention content	Topics covered, services delivered, referrals made during couple visits	
PROCESS MEASURES			All intervention participants at follow-up

Participation	Number of couple home visits completed, number of HIV self-tests received/used		
Social consequences	Positive and Negative Life Events measures[142]		
Acceptability	Satisfaction with intervention components, intervention content, and mode of delivery, attitudes toward PrEP and HIV self-testing		
SECONDARY HEALTH OUTCOMES	Viral suppression	Viral Load < 200 copies (undetectable)*	All HIV-positive participants at baseline and follow-ups
	HIV-free child survival	Child alive and HIV-free at 18 months after the birth*	

* Measures to be confirmed through medical records

536

537

538 Inclusion/exclusion criteria

539 Our inclusion criteria are: (a) women at 36 weeks of pregnancy or less (b) 15 years of age or older (c)
 540 has been offered HIV testing at ANC, (d) is currently in a stable relationship with a male partner and
 541 living with that male partner, (e) has not yet participated in couple HIV testing during this pregnancy,
 542 and (f) not in an HIV-positive concordant relationship Male partners are the person identified by the
 543 pregnant woman as her primary male partner and should also be 15 years of age or older.

544

545 STATISTICAL/ANALYSIS PLAN

546 Sample size and power calculations

547 The couple testing uptake outcome (primary outcome) will be assessed including both HIV-positive and
 548 HIV-negative women/couples. All three arms will be compared with each other (3 comparisons), so our
 549 Type I error rate is $0.05/3 = 0.017$ (two-sided). With three repeated measurements (baseline, 3 months,
 550 and 12 months) and compound symmetry
 551 covariance structure, correlation between
 552 the observations on the same subject was
 553 assumed to be 0.50. With N=300 couples
 554 in each arm, our study will have >80%
 555 power to detect statistically significant
 556 differences in couple testing uptake of 30-
 557 40% either intervention arm and 23% in
 558 the control arm (Table 2). We
 559 conservatively used rates that are lower
 560 than proportions observed in the R34
 561 study and studies of HIVST kits with
 562 pregnant women. The secondary

563 outcomes are HIV-free child survival at 18 months and maternal viral load suppression at 18 months.
 564 HIV-free child survival up to 18 months will be assessed only in HIV-positive women with live births,
 565 with approximately N=200 in each arm. Based on prior estimates from sub-Saharan Africa,[161, 162]
 566 we expect proportions $\geq 90\%$ of HIV-free survivors in each arm. As there would be 2 comparisons (each
 567 intervention arm versus the control arm), we set our Type I error rate to $0.05/2 = 0.025$ (two-sided) when
 568 calculating power. If Arm 3 has a survival rate of 91%, the study will have power > 80% when Arms 1
 569 and 2 have survival rates of 98% or higher. The other secondary outcome of maternal viral load
 570 suppression at 18 months will be assessed only in HIV-positive women with around N=200 in each
 571 arm. From Table 2, if Arm 3 has a maternal viral load suppression rate of 85%, the study will have
 572 power > 80% when Arms 1 and 2 have maternal viral load suppression rates of 95% or higher. We
 573 used PASS software for these calculations (NCSS, version 11).

574

575 Data analysis

576 **Primary analyses to address Aim 1:** We will use all longitudinal measures of couple testing in a
 577 marginal model to compare rates among the three study arms. We will use a marginal modeling
 578 approach because our primary interest is to estimate the population-average effect of intervention
 579 participation on each outcome rather than the effect for a hypothetical average subject or couple.

Table 2. Statistical Power for Comparison of Outcomes Among Study Arms				
Couple Testing Uptake (assuming 23% uptake in the standard care arm (Arm 3)				
Proportion (%) of CHTC uptake in Arm 1 or 2	31	33	35	37
Corresponding Odds ratio (ref=Arm3)	1.50	1.65	1.80	1.97
Power (%) to detect a sig. difference among Arms at 0.017 level, auto-correlation (rho)=0.50	63	84	95	99

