24 attending antenatal clinics (533 HIV-positive and 267 HIV-negative at baseline) and their primary male
25 partners. We will randomize couples to home-based visits, multiple HIV self-test kits, or the standard
26 care of male partner invitation letters and follow them up for 18 months postpartum to (a) determine the
27 impact of a couples-focused home-based intervention on our primary outcome of couple HIV testing for
28 pregnant women and their male partners (assessed through proportion reporting couples testing, yield
29 of new HIV+ diagnoses of male partners, and identification of new sero-discordant couples) as
30 compared to HIV self-test kits for couples and standard care; (b) examine the impact of the intervention
31 on HIV prevention behaviors (PrEP and condom use), facility delivery, and postnatal healthcare
32 utilization for all participants; as well as secondary health outcomes of maternal VL suppression, and
33 HIV-free child survival up to 18 months for couples living with HIV; as compared to HIV self-test kits for
34 couples and standard care and; (c) compare the cost-effectiveness of the home-based couples
35 intervention to less resource-intensive strategies of standard care and HIV self-test kits for couples.
36 Despite its promise, a home-based intervention may require more resources and it is important to
37 assess whether it offers greater value for money than other strategies, which may cost less but be less
38 impactful. This theory-based couples intervention has strong potential to increase couples HIV
39 testing and use of essential health services by pregnant women and their male partners.
40

41 **LAY SUMMARY**

42 HIV-related maternal deaths and HIV infection among infants remain unacceptably high across sub-
43 Saharan Africa. This is despite the potential for antiretroviral therapy (ART) to improve maternal health
44 and reduce mother-to-child transmission of HIV. This is particularly true in Kenya, where antenatal care
45 attendance is high but crucial drop-offs occur in uptake of and adherence to key maternal and child
46 health and prevention of mother-to-child transmission (PMTCT) services. Many pregnant women avoid
47 couple HIV testing or do not adhere to PMTCT services because they fear negative consequences of
48 HIV for their relationship with their male partner. Men can play a crucial decision-making and supportive
49 role for family health, but male partners of pregnant women in Kenya are poorly engaged in PMTCT.

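### Nothing in the plan keeps the arm from interviewers when they ask whether the couple tested together, and record confirmation covers the gap only in part.

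*Combined protocol and SAP*

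**What the plan says.** - **Outcome.** The Abstract and Aim 1 describe the primary outcome as couple HIV testing for "pregnant women and their male partners (assessed through proportion reporting couples testing, yield" of new male diagnoses, and new discordant couples). In Table 1 (Factors to be Assessed in Data Collection) it is "Couples HIV testing uptake during observation period (Y/N"), with an asterisk that means "Measures to be confirmed through medical records".
- **Instrument.** Under Data collection and measures, the follow-up questionnaires at 3 and about 12 months repeat the baseline constructs "as process and outcome measures, and be administered on tablets in the" participant's own language.
- **Who asks.** They are given in the participant's "language during research visits or through phone by gender-matched independent interviewers". Sources of materials adds that HIV test counselors are separate from interviewers. Neither statement says that interviewers are unaware of the arm.
- **Process items.** Table 1 lists "Number of couple home visits completed, number of HIV self-tests received/used" and satisfaction with intervention components, for "All intervention participants at follow-up".
- **Other sources on testing.** Brief phone surveys ask both partners about testing at 8 weeks after enrollment and around 6 months after the birth, and an 18-month call covers couples testing again. "Medical records will be abstracted to obtain objective (non self-report) data on" service use and health outcomes for everyone. At each Arm 1 visit the lay health workers enter testing uptake and result on a couple visit form.

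**The concern.** The participants' arm cannot be hidden from them. It can be kept from the interviewer until the primary outcome has been recorded, and the plan does not provide for this. A module on home visits completed and satisfaction with components applies only to Arms 1 and 2. Whoever administers it learns, or already knows, that the couple is in one of those arms, and its absence points to Arm 3.

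Whether two people tested together is open to probing and interpretation, most of all for kits used at home. More probing or more lenient coding in Arms 1 and 2 would look like an effect in the two comparisons with standard care. The 0.017 threshold controls chance across three comparisons. It does nothing about a systematic shift in one direction.

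**Working it through.** **1. The plan's own figure.** Table 2 gives power for 23% against 31, 33, 35 and 37% at two-sided 0.017, with 300 couples per arm, three measurements and rho 0.50. Effective n per arm = N·m / (1 + (m − 1)·rho) = 300·3 / (1 + 2·0.5) = 450. A pooled two-proportion test then gives 62.5, 83.1, 94.5 and 98.7%, against the stated 63, 84, 95 and 99%. The figures reproduce, so the same test is a fair basis for a sensitivity check.

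**2. Inputs to the check.**
- True uptake 23% in every arm (the Table 2 control rate).
- Two-sided 0.017, so z = 2.387.
- 267 couples per arm as planned, or 221 after 17% loss (Sample size).
- Differential over-reporting d: *not in the documents*; assumed at 3, 5 and 8 points in both intervention arms.
- Simplifications: one yes/no per couple, and no correction by records.

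Among the 77% who truly did not test, these shifts mean 3/77 = 3.9%, 5/77 = 6.5% and 8/77 = 10.4% recorded as couple testers.

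**3. One comparison, worked for d = 5 points, n = 267.**
- Mean proportion (0.23 + 0.28)/2 = 0.255.
- SE under the null = √(2·0.255·0.745/267) = 0.0377.
- SE under the shift = √((0.23·0.77 + 0.28·0.72)/267) = 0.0377.
- (0.05 − 2.387·0.0377)/0.0377 = −1.06, so the chance of rejection is 14.4%.

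**4. At least one of Arm 1 or Arm 2 falsely beating Arm 3.** The two comparisons share a control arm, so this was simulated (pooled z-test, at least 200,000 trials).

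| Shift in both arms | 267 per arm | 221 per arm |
|---|---|---|
| none | 1.6% | 1.6% |
| 3 points | about 10% | about 9% |
| 5 points | about 23% | about 20% |
| 8 points | about 54% | about 46% |

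The no-shift entry counts only results favouring an intervention arm. Counting both directions it is 3.2%.

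**5. Closer to the planned repeated-measures model.** With rho 0.50 and three measurements, 267 per arm gives an effective n of 267·3/2 ≈ 400. The per-comparison risk at 3, 5 and 8 points is then 8.1, 22.2 and 56.5%, against 1.7% with no shift. For a single yes/no it is 5.8, 14.4 and 38.0%. The one-answer simplification in step 4 therefore does not exaggerate the result.

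**6. What record confirmation can do in each arm.**
- *Arm 1:* testing at a home visit is documented by the staff who deliver the intervention.
- *Arm 2:* only a reactive self-test is directed to a clinic, so a non-reactive couple self-test at home need not leave a clinic record.
- *Arm 3:* testing is chiefly clinic-based, so a clinic record is likely.

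Confirmation is thus weakest where the outcome depends most on what the participant says. No rule states whether a record overrules a report.

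**The case against.** The case on the other side is substantial.

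- **The outcome is not self-report alone.** A reader of the Abstract might infer that it is, but Table 1 has it confirmed through medical records. This stands. Confirmation reduces the risk by an unknown amount, and unevenly across arms.
- **Testing is also asked elsewhere.** No process items are listed for the phone surveys, the 8-week call precedes any follow-up questionnaire, and Data analysis uses all longitudinal measures. This stands as dilution. Those calls are self-reports too, and the power calculation names baseline, 3 and 12 months as its measurements.
- **Arm knowledge at the moment of asking is an inference.** Item order is not given, so process items may already come last. A reader might also assume that the same interviewer returns at 12 months; no section says so. Both points stand: the documents show that nothing prevents arm knowledge, not that it occurs.
- **Partners are interviewed by different people** who are told not to compare answers (Loss of confidentiality), so one interviewer does not settle both reports. This stands, but the plan does not require the two reports to agree.
- **Self-test use is assessed in all three arms** (Limitations), so that item alone does not reveal the arm. Home visits and satisfaction with components still do.

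**Conclusion.** The concern holds in a limited form. Outcome and arm-specific process items share an interviewer-administered questionnaire, no section conceals the arm, and record confirmation is undefined and unequal across arms. An interviewer can therefore know the arm when recording the primary outcome.

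Over-reporting of 3 to 8 points in both intervention arms would raise the chance of a false finding for an intervention from 1.6% to between about 10% and 54% at 267 per arm (about 9% to 46% at 221). These figures rest on an assumed shift, on 23% true uptake everywhere and on no correction by records. A reader might take them as the trial's actual error rate. The documents do not support that, because they give neither the size nor the direction of any shift. The comparison of Arm 1 with Arm 2 is less exposed, since both receive process items. The change is worth making because it is cheap and the outcome is the primary one.

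**What to change.** Amend Data collection and measures for all remaining interviews, in person and by phone:

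1. Put the HIV-testing items first and lock the answers.
2. Do not show the arm to the interviewer before the lock.
3. Open the process module last.
4. Record which interviews used the new order.

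Add to Data analysis a sensitivity analysis of the primary outcome that counts only couple tests reported separately by both partners or confirmed by records. State what counts as confirmation in each arm, since clinic records alone would under-count Arm 2.

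*Cost:* reprogramming of the tablet and phone scripts and one added analysis, with no extra visits or staff. Enrollment was already under way in 18 clinics at this version, so some follow-up may have been collected in the existing order. The order would then change mid-trial, but in all arms alike, and blocked randomization keeps the arms about equal over time. Participants know their arm and may reveal it, so their own arm-related reporting remains.
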